## **The Modulation of Cerebral Pain Responses Using Desipramine in the Treatment of Irritable Bowel Syndrome (IBS)**

### **7.5.4: Research Plan**

#### **A. Statement of Hypotheses and Specific Aims**

Irritable bowel syndrome (IBS) is a common abdominal pain disorder diagnosed by symptom-based criteria (Rome III). Since there are no objective measures available to establish a formal diagnosis, IBS likely encompasses a biologically heterogeneous group of patients with distinct pathophysiology. The majority of studies examining the mechanistic basis of IBS have focused on bowel-specific factors. Recent neuroimaging studies using functional magnetic resonance imaging (fMRI) have demonstrated abnormal brain activation patterns with noxious visceral stimulation in some, but not all, IBS patients. Regions comprising the homeostatic afferent processing network (HAPN), important to cognitive and affective interpretation of pain signals, demonstrate striking visceral pain response abnormalities in many IBS subjects. It is possible that HAPN pain responses have pathophysiologic relevance in a subset of IBS patients. We thus seek to characterize a putative IBS subgroup—those with abnormal HAPN visceral pain activations (IBS-HAPN).

A clearer understanding the role of the HAPN in IBS pathophysiology would be of substantial clinical importance on two accounts. First, centrally-acting antidepressant therapies, shown to influence the HAPN responses to visceral pain, are effective in only one-half of IBS subjects. The identification of objective features which predict IBS response to antidepressant therapy (i.e., HAPN pain responses patterns) would potentially allow for the development of more rational IBS treatment approaches. Second, abnormal HAPN pain activations may have broader implications in IBS pain experiences. One-third of IBS patients have comorbid somatization, a condition exemplified by multiple unexplained pain syndromes. It is possible that in IBS patients with somatization, the abnormal HAPN activations observed with visceral stimulation may also occur with non-visceral (somatic) noxious stimuli.

**The overarching hypothesis of this proposal is that aberrant brain responses to visceral pain signals within the homeostatic afferent processing network (HAPN) represent the primary mechanism responsible for bowel pain experiences in a subset of IBS patients (IBS-HAPN).** Our preliminary data has identified a pattern of brain activation differences within the HAPN following visceral stimulation in IBS subjects compared to healthy controls. Using fMRI, I will further characterize the HAPN pain responses of IBS-S subjects to additional non-visceral stimuli and following antidepressant therapy. I predict that this protocol will reveal a pattern of increased HAPN pain activations to both visceral and somatic stimuli—activations that are refractory to antidepressant pharmacotherapy. Ultimately these findings will demonstrate the mechanistic importance of the HAPN to pain experiences in the IBS-S subgroup.

*These goals will be realized through the pursuit of the following Specific Aims:*

**Specific Aim 1. To compare HAPN activations following noxious somatic stimulation in IBS subjects based on the presence of somatization.**

*Hypothesis 1:* As a result of a generalized abnormal pain response within the HAPN, IBS-S subjects will demonstrate greater HAPN activations with noxious somatic stimuli, compared to IBS subjects with no somatization and healthy controls.

**Specific Aim 2. To compare the effects of antidepressant therapy HAPN activations following noxious visceral stimulation in IBS subjects based on the presence of somatization.**

*Hypothesis 2:* Consistent with clinical refractoriness to antidepressant treatment, IBS-S subjects will demonstrate a persistent pattern of abnormal HAPN visceral activations following desipramine therapy, whereas significant improvements in HAPN visceral activations will be observed in IBS subjects with no somatization following antidepressant therapy.

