Adapted from Price, DD. *Science* 2000.

these findings, though the magnitudes of these IBS-healthy control differences in HAPN activation are less consistent across studies. In part, these observations may reflect significant protocol differences, including the use of different imaging modalities (PET and fMRI), study designs (noxious stimulation type, intensity, and duration) and data analysis methodologies. However, another likely explanation is the mechanistic heterogeneity that exists within IBS patients when examined as a single population. It is likely that only a subset of IBS patients experience significant HAPN overactivation with noxious visceral stimulation. Thus, when HAPN pain responses are examined in all IBS subjects, the inclusion of IBS subgroups in which HAPN overactivation is not mechanistically-relevant may bias findings toward the null.

The HAPN is not only important to the emotional and cognitive responses to visceral pain, but likely is also relevant to somatic pain experiences in somatization syndromes. A study by Chang *et. al.* found that in IBS subjects, a greater HAPN response within ACC was seen in response to somatic stimulation, but only in those with comorbid fibromyalgia (a somatization syndrome). This finding supports my hypothesis that IBS subjects with somatization may experience activations of the HAPN with a broader spectrum of noxious stimuli, including painful somatic stimuli.

The recognition of specific a IBS population in which CNS pain processing abnormalities have mechanistic relevance would represent an important step in advancing our

**IBS Subjects (n=18) and controls following rectal balloon distension.** IBS subjects demonstrate greater activity within the homeostatic afferent processing network (HAPN) in response to visceral distension compared to controls. (from Mertz, *et al.*)

[figure not shown]
understanding of IBS pathophysiology. Recently, I completed a preliminary study to examine the influence of somatization on cerebral activations within the HAPN in an IBS population based on the degree of somatization present (see Preliminary Studies, Section C). *This work successfully demonstrated significant differences in HAPN activations in IBS-S compared to IBS-no S subjects, strongly suggesting that abdominal pain experiences in IBS-S subjects are a consequence of abnormal HAPN responses to afferent intestinal sensory input.*

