### Intervention

Functional MRI studies were performed while applying simultaneous visceral stimulation (rectal balloon distension) at low- (25-mmHg) and higher-pressure (50-mmHg) levels in random order following established protocols. Subjective ratings for distension discomfort were assessed for each distention using a 10-point Likert scale at the end of each distention sequence.

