## Findings

**Clinical features and subjective pain ratings:** 24 right-handed female subjects (8 in each study group) underwent fMRI during the rectal balloon distention protocol from April 2007 to June 2008. A summary of the clinical features and subjective pain ratings in response to the balloon distentions are reported in Table xx. Subject ages were not significantly different across study groups. However, there were significant differences in IBS symptom ratings between the IBS-S and IBS-No S groups, with greater symptom severity, frequency, and global symptom burdens reported by the IBS-S group. Depression and anxiety scores on the Beck Inventories also were significantly higher in the IBS-S group compared to IBS-No S and healthy controls. Subjective experiences with the low-pressure (25 mm-Hg) rectal balloon distentions trended toward significantly greater discomfort reporting in the IBS-S group ( $p=0.3$ ), but no differences were appreciated across groups with the higher pressure (50-mm Hg) distentions. (Table 1).

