### **Significance of findings**

In this study, IBS subjects clearly differed in their HAPN brain responses to visceral stimulation compared to healthy controls. A similar pattern of HAPN activation in IBS has been observed in several other studies, suggesting that dysfunctional affective and cognitive processing of visceral pain signals within the HAPN may be of mechanistic relevance to IBS symptom experiences. Hypothesizing that these HAPN pain responses are of particular importance to IBS subjects with comorbid somatization, a similar comparison of HAPN visceral activations was performed between IBS-S and IBS-No S subjects. In this small study sample, significantly greater activations of many of these same HAPN regions were observed in the IBS-S subjects compared to their IBS-No S counterparts. This finding supports my hypothesis that abnormal HAPN processing of afferent visceral signals may be of greater pathophysiologic relevance to the subset of IBS patients that have comorbid somatization.

An important HAPN region that demonstrated greater activation in the IBS-S subgroup was the perigenual portion of the anterior cingulate cortex (ACC). The ACC is the region most consistently activated by visceral stimulation, and thus is regarded by some as “the visceral pain center”. Electrical stimulation of this region results in a potent fear response, suggesting the key role of the ACC in emotional responses to aversive stimuli. This region additionally has prominent descending connections to the dorsal vagal complex and periaqueductal gray, and as such is believed to play a central role in the endogenous modulation of pain and autonomic tone. The ACC influence on autonomic function could explain the alterations in bowel patterns often accompanying IBS pain experiences. Similarly, the right insular cortex (IC) demonstrated significantly greater activation in the IBS-S subgroup. Studies have shown that lesions within the IC result in modulation of the affective pain response, but not visceral sensory responses. This region, along with the ACC, also has been shown to activate in response to viewed fearful faces (negative emotional condition). Together, these findings suggest that abnormal right IC and ACC affective responses to noxious visceral stimuli may be important to IBS-S symptom experiences.

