- c) Somatic Symptoms Inventory (SSI) (Part C): The SSI is a self-report questionnaire composed of 26 bodily complaints drawn from the hypochondriasis scale of the Minnesota Multiphasic Personality Inventory and the Hopkins Symptom Checklist somatization scale.
- d) SOMS-7 (Part D) is a 7-item instrument for the evaluation of treatment effects in somatoform disorders. It covers all somatic symptoms mentioned as occurring in somatization disorder, according to DSM-IV and ICD-10.
- e) Gastrointestinal Symptom Rating Scale for IBS (GSRS-IBS) (Part E): The Gastrointestinal Symptom Rating Scale is a disease-specific instrument that includes 15 items combined into five-symptom clusters addressing different gastrointestinal symptoms. The five-symptom clusters depict reflux, abdominal pain, indigestion, diarrhea and constipation. The GSRS has a seven-graded Likert type scale where 1 represents absence of bothersome symptoms and 7 very bothersome symptoms. The GSRS is well documented to be reliable and valid and norm values for a general population are available.
- f) Life-Stress Questionnaire. (4) Additional questionnaire measures
  - a) SES Ladder (SES-L)
  - b) Brief Pain Inventory (BPI)
  - c) Hospital Anxiety and Depression Scales (HADS)
  - d) Coping Strategies Questionnaire-Catastrophizing scale (CSQ-C)
  - e) IPIP Neuroticism and Extroversion scales (IPIP-NEO)
  - f) Early Trauma Inventory-Self Report (ETISR)

g) Positive and Negative Affect Scales (PANAS-SF)

(5) Diet Assessment

a) Harvard School of Public Health Food Frequency Questionnaire (FFQ):

<https://regepi.bwh.harvard.edu/health/FFQ/files/2007%20BOOKLET%20FFQ.pdf>

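### The plan says its findings will demonstrate that brain activation is the mechanism of bowel pain, but both aims compare activation between somatization groups and no planned analysis relates activation to pain

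*Combined protocol and SAP*

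**What the plan says.** Section A states the overarching hypothesis causally: abnormal HAPN responses "represent the primary mechanism responsible for bowel pain experiences in a subset of IBS patients (IBS-HAPN". It then says what the study will deliver: "Ultimately these findings will demonstrate the mechanistic importance of the HAPN to pain experiences in the IBS-S subgroup". Section B.3 already reads the pilot in this way, "strongly suggesting that abdominal pain experiences in IBS-S subjects are a consequence of abnormal HAPN responses to afferent intestinal sensory input".

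The planned analyses are narrower.

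- **Aim 1** (section D, Design and Methods): the primary endpoint is HAPN activation after somatic stimulation in 20 IBS-S, 20 IBS-No S and 20 healthy controls.
- **Aim 2** (section D): the primary endpoint is visceral activation after desipramine, compared between IBS-S and IBS-No S.
- **Image model** (Data Analysis and Sample Size Calculations): it has three event types (low distension, high distension, somatic stimulus) and no pain term.
- **Symptom severity** (Aim 1, Pitfalls/Limitations): it enters extra ANOVA models so that it can be ruled out as an explanation for the group difference. Aim 2 adopts the same handling.

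Bowel symptom measures are planned. For one of them, the GSRS-IBS, section 3 (Assessment measures) says: "The five-symptom clusters depict reflux, abdominal pain, indigestion, diarrhea and constipation". In the pilot, discomfort was "assessed for each distention using a 10-point Likert scale". The main-study distension protocol mentions no such rating.

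**The concern.** A difference in activation between somatization groups is what the hypothesis predicts, but other explanations predict it too. Activation could be a marker of somatization with no bearing on bowel pain. It could also be a consequence of stronger signals from the gut: section B.5 and Figure 5 expect IBS-No S patients to show raised HAPN activation to visceral stimuli for that reason. Or part of it could be modulatory, since the pilot discussion says that the anterior cingulate "is believed to play a central role in the endogenous modulation of pain and autonomic tone". The group comparison does not separate these explanations, and the plan contains no analysis in which patients with more activation are asked whether they have more pain.

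The use of severity as a confounder adds a second difficulty. If activation causes pain, severity lies downstream of activation. Adjusting the group difference for it then removes part of the effect that the hypothesis describes.

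At stake is the headline conclusion. The group comparisons remain valid as group comparisons, but the causal statement in section A would not follow from them.

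**Working it through.** **Inputs.** Table 1 (section C) gives means and SDs, with "24 right-handed female subjects (8 in each study group) underwent fMRI". Group sizes for the main study are from Aim 1. A two-sided 5% level and 80% power are my assumptions.

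**1. Reproducing the printed p-values.** One-way ANOVA from summary data, F = MSB/MSW on 2 and 21 df:

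- 50 mm Hg: means 5.1, 4.5, 4.6; SDs 2.0, 2.2, 2.2. MSB = 8 × (0.367² + 0.233² + 0.133²)/2 = 0.83; MSW = (4.00 + 4.84 + 4.84)/3 = 4.56; F = 0.18, p = 0.84 (printed 0.8).
- 25 mm Hg: means 3.0, 2.8, 2.0; SDs 1.4, 1.4, 0.9. MSB = 2.24; MSW = (1.96 + 1.96 + 0.81)/3 = 1.58; F = 1.42, p = 0.26 (printed 0.3).

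Both agree.

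**2. The contrast that matters, IBS-S minus IBS-No S.** SE = s_p × √(2/8), 14 df, t critical value 2.145:

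| Measure | Difference | s_p | SE | 95% CI | p |
|---|---|---|---|---|---|
| Rating, 50 mm Hg | 0.6 | 2.10 | 1.05 | -1.7 to 2.9 | 0.58 |
| Rating, 25 mm Hg | 0.2 | 1.40 | 0.70 | -1.3 to 1.7 | 0.78 |
| IBS symptom severity | 2.7 | 2.39 | 1.20 | 0.1 to 5.3 | 0.04 |

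With 8 per group and SD 2.1, power (noncentral t) is 14% for a true 1-point difference and 43% for 2 points.

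At 25 mm Hg the larger gaps are to controls: 3.0 - 2.0 = 1.0 point for IBS-S and 2.8 - 2.0 = 0.8 for IBS-No S. The Findings text calls the three-group p = 0.3 a trend towards more discomfort in IBS-S. The 0.2-point gap between the IBS groups does not bear that out.

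**3. Pilot activation.** In the IBS-S v IBS-No S columns of Table 2, 7 of 10 region-hemispheres have p < 0.05, and the same seven have Z above 1.96. The three that do not are the left insula, left prefrontal cortex and left thalamus.

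**4. Effect of adjusting for a downstream variable.** As an illustration, suppose group acts on activation (effect a), activation acts linearly on pain, and there is no other path. Let ρ be the within-group correlation of activation with pain. The group effect on activation adjusted for pain is then a × (1 - ρ²). With ρ = 0.43 it falls by 0.43² = 18%; with ρ = 0.59, by 0.59² = 35%.

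**5. What a baseline activation-pain analysis could detect.** Fisher z: atanh(r) = (1.960 + 0.842)/√(n - 3).

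- n = 40: 2.802/√37 = 0.461, r = 0.43. Allowing one degree of freedom for group: 2.802/√36 = 0.467, r = 0.44.
- n = 20: 2.802/√17 = 0.680, r = 0.59.

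Requiring the interval within 20 IBS-S to exclude zero would have power Φ(atanh(r) × √17 - 1.96): 25% at r = 0.3 and 42% at r = 0.4.

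**The case against.** Five points can be made for the plan.

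- **The pilot ratings do not show equal pain.** A reader might infer that groups with different activation felt the same pain. The documents do not support that. The text says only that "no differences were appreciated across groups with the higher pressure (50-mm Hg) distentions", and the interval at 50 mm Hg runs to 2.9 points on a 10-point scale. Pilot activation was also pooled over both pressures, whereas ratings are given by pressure. This stands.
- **Clinical symptoms point the plan's way.** The hypothesis concerns bowel pain, not balloon ratings, and IBS-S had worse severity (6.9 v 4.2, p = 0.04), frequency (9.1 v 2.4, p = 0.006) and global burden (7.5 v 3.2, p = 0.005). This stands as compatible evidence. But depression (19.1 v 3.5) and anxiety (19.9 v 3.1) scores differed sharply too, and the pilot discussion itself names bowel and mood symptoms as potential confounders.
- **The severity-adjusted models would yield an association.** They normally would, so it is too strong to say that nothing in the plan touches the question. The plan nevertheless frames that term as something to exclude and does not interpret it.
- **The wording elsewhere is hedged.** The section D Overview and the Aim 1 interpretation say only that HAPN responses may or could have relevance, different outcomes receive different interpretations, and section A refers to the whole predicted pattern over both aims. A reader might infer that the causal conclusion would be drawn whatever the result; the documents do not go that far. The unhedged statements in sections A and B.3 remain.
- **A regression cannot establish cause.** A positive slope would also appear if more pain evoked more modulatory activity. This stands, and it is why the added analysis should be supportive and its conclusion limited to association. Nor do the documents make a compensatory reading equally likely: the same discussion ties the cingulate to visceral pain and fear, and section B.4 cites reduced cingulate activation on a related tricyclic.

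**Conclusion.** The concern holds in a limited form. Aims 1 and 2 as planned can show that activation differs by somatization group. They cannot demonstrate that HAPN activation is the primary mechanism of bowel pain, because no analysis uses pain as an outcome or correlate of activation. A reader might go further and say that Aim 1 cannot support the hypothesis at all. That is too strong: a group difference would be compatible evidence, though neither sufficient nor specific.

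The pilot leaves the question open: a clear activation difference, no detected rating difference with wide intervals, and a clinical symptom difference entangled with mood. The loss from adjusting for severity (18% to 35% in the illustration) depends on the assumed causal chain and correlations. The detectable correlations assume one outcome, one region and no multiplicity correction. No primary endpoint, sample size or primary test needs to change.

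**What to change.** 1. Pre-specify one supportive baseline regression in the 40 IBS subjects. The outcome is the GSRS-IBS abdominal pain cluster. The predictor is visceral Delta S/S at 50 mm Hg in the anterior cingulate, the region used for the sample size calculation. Include group and group × activation. Report pooled and within-group slopes with 95% CIs and no significance gate. State in advance how the two hemispheres are combined, and confirm that the GSRS-IBS is completed at baseline.
2. Report the severity-adjusted ANOVA models beside the unadjusted ones, noting that severity may lie downstream of activation.
3. Restate sections A and B.3 so that the conclusion is a group difference in activation and, if seen, an association with bowel pain, not a demonstrated cause.
4. In the pilot Findings, remove the description of p = 0.3 as a trend towards greater discomfort in IBS-S.

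The cost is one regression on measures already planned, plus wording. The downsides are limited precision, especially within 20 IBS-S, and a mechanistic claim that becomes harder to make.

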## ***Regional activations within the HAPN by study group***

[figure not shown]
Consistent with findings previously reported in the literature, during noxious visceral stimulation a significant difference in a HAPN brain region activations was seen in comparing IBS subjects and healthy controls (Table 2 and Figure 7). Between-comparison of HAPN activations in the IBS-S and IBS-No S groups revealed significantly greater activation of the right prefrontal cortex, insula, and thalamus in the IBS-S subjects. The

IBS-S subjects also were found to have greater activation of the bilateral anterior cingulate and orbitofrontal cortices compared to their IBS-No S counterparts.

[figure not shown]
**Table 2: Regional differences in cerebral activations within the homeostatic afferent processing network (HAPN) in response to visceral stimulation in IBS-S subjects compared to controls, and IBS-S compared to IBS-No S subjects.**

Region	Hemisphere	Coordinates (x,y,z)*	All IBS vs. Controls		IBS-S vs. IBS-No S	
			Z	p	Z	p
Anterior cingulate cortex	Left	-8, 38, 16	2.91	0.004	2.67	7.3 x10 
	Right	9, 34, 11	2.19	0.02	4.15	7.6 x10 
Insula	Left	-39, 2, 7	5.20	9.7 x10 	1.09	0.27
	Right	32, 23, 10	5.47	2.8 x10 	2.33	0.02
Orbitofrontal cortex	Left	-25, 13,-10	4.27	1.9 x10 	3.13	0.001
	Right	34,22,-3	4.82	1.4 x10 	4.84	6.5 x10 
Prefrontal cortex	Left	-41, 40, 11	4.87	5.4 x10 	1.37	0.16
	Right	41, 50, 5	5.78	3.5 x10 	4.17	2.4 x10 
Thalamus	Left	-19, -22, 11	5.58	1.2 x10 	1.51	0.12
	Right	12, -8, 11	4.02	5.8 x10 	2.09	0.003

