**Specific Aim 2. To compare the effects of antidepressant therapy HAPN activations following noxious visceral stimulation in IBS subjects based on the presence of somatization.**

Rationale: Case-control and randomized clinical trial data have established that somatization predicts symptom responses to IBS therapy with the tricyclic antidepressant desipramine. Specifically, IBS-S subjects are more refractory to antidepressant therapies, while IBS-No S subjects have better overall responses to the same treatment. A recent study has demonstrated improvements in HAPN visceral activations (anterior cingulate cortex) following desipramine therapy in an IBS cohort. Given these observations, the goal of this Aim is to assess whether differences in visceral HAPN activation patterns following desipramine treatment can be detected in IBS-S and IBS-No S subjects.

Design and Methods: The proposed study implements open-label desipramine therapy in 40 IBS (20 IBS-S and 20 age-matched IBS-No S) subjects. Participants from Aim 1 will be invited to continue on to open-label therapy in Aim 2. IBS-S and IBS-No S subjects will receive a 4-week treatment course with the tricyclic antidepressant desipramine (DES), as detailed in section 2.D., below. Subjects will undergo a fMRI protocol with noxious visceral and somatic stimuli as in Aim 1 at baseline, and then immediately following the 4-week desipramine therapy. Subjects will undergo baseline, and post-therapy assessment of psychiatric comorbidity (depression/anxiety) and IBS symptom severity (as described in 3.A. and 3.B., below). The primary endpoint is differences in visceral stimulation-induced brain activations of the HAPN on fMRI, ascertained between-groups following desipramine therapy. The proposed study design is outlined in Figure 9.

[figure not shown]
**Figure 9. Overview of study design for Specific Aim 2.** IBS patients with somatization (IBS-S) and without somatization (IBS-No S) will be identified. A baseline fMRI protocol (as in Aim 1) will be obtained at baseline, followed by a 4-week, open-label treatment with desipramine. A second fMRI protocol will be performed post-desipramine therapy at week 4. The primary endpoint of interest is post-treatment differences in visceral HAPN activations between IBS-S and IBS-No S subjects.

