Analysis/interpretation: *Consistent with the clinical refractoriness to antidepressant therapy observed in IBS-S subjects, it is hypothesized that IBS-S subjects will exhibit a persistent pattern of abnormal HAPN activations in response to visceral stimulation following desipramine therapy.* By comparison, it is hypothesized that the IBS-No S group will exhibit decreases in HAPN activations in the post-treatment fMRI protocol (Figure 10, below). Region of interest two-way ANOVA models will be developed in comparing  $\Delta$ baseline-DES activations, with IBS Group (IBS-S and IBS-No S) as a between-subject factor. If the stated hypothesis is supported by the fMRI findings, it would suggest that the persistent HAPN activations in response to visceral afferent signals may result in the less robust clinical responses to desipramine therapy in the IBS-S. This finding would be an important addition to the existing literature, providing both insight into the central mechanisms involved in IBS antidepressant response, and also into the specific relevance of HAPN pain responses to the IBS-S subgroup.

Conversely, should HAPN activations be found to improve in both IBS groups following desipramine therapy, the possibility that HAPN visceral activations are indeed partially refractory to desipramine in IBS-S, but the detected between-group differences (IBS-S vs. IBS-No S) in post-desipramine changes in HAPN activation were smaller than expected, and thus not statistically significant. If this were the case, the ANOVA analyses would be likely demonstrate statistical trends between the IBS groups, and enrollment of additional subjects would be considered if feasible following power calculations. This additional step might lead to findings which allow for rejection of the null hypothesis.

[figure not shown]

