(Delta S/S) will be the metric that is used. To statistically evaluate this, ROI analysis will be conducted in anatomically constrained areas along with voxel-by-voxel analysis. Both ROI-directed and voxel-by-voxel repeated measures ANOVAs (using parameters described below) are done across subjects using model estimates as inputs. Interaction effects and other activations resulting from specific comparisons of a subset of the events will be reported at an uncorrected threshold of  $p < 0.001$  for descriptive purposes. For the insular cortex, prefrontal cortex, orbitofrontal cortex, anterior cingulate cortex, and thalamic nuclei, predetermined ROIs will be used and will include any activations within these regions. A small volume correction will be applied, in keeping with the *a priori* hypotheses regarding these regions. Predetermined ROIs from the HAPN in Talairach space will be drawn using the Talairach atlas coordinate system^99 and the software ANALYZE™ will then be applied to all the participants. Regions which would not be expected to differ between the study populations will also be selected for analysis, and will provide internal activation standards to provide for the specificity of the findings (i.e., control regions). All selected ROIs will be used as a mask to constrain the regions in which test for differences are conducted. These regions will be used as a mask in an overlay on functional datasets to test the

hypotheses. Only areas with significant F-values on the ANOVA and falling within these regions will be used in statistical analyses. There will be 3 event types included in the model, resulting from the combination of all possible stimulus and response conditions: Visceral-Low distention (25-mm Hg), Visceral-High distention (50-mm Hg), and the Somatic stimulus. Voxel-by-voxel analyses will be conducted primarily to ensure that unpredicted differences a priori ROIs which are significant are not overlooked.

[figure not shown]

Figure 13: Study power as a function of sample size and effect.

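### Aim 2 is stated on two scales, post-treatment level and absolute change, and a higher IBS-S baseline can push them to opposite conclusions

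*Combined protocol and SAP*

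**What the plan says.** Hypothesis 2 (section A) is that "IBS-S subjects will demonstrate a persistent pattern of abnormal HAPN visceral activations following desipramine therapy, whereas significant improvements in HAPN visceral activations" will be seen in patients without somatization. It names no scale. Three further parts of the combined protocol and SAP bear on how it is tested.

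- **Endpoint.** Specific Aim 2, Design and Methods, defines the primary endpoint as activation differences "ascertained between-groups following desipramine therapy". The Figure 9 legend repeats this: "The primary endpoint of interest is post-treatment differences in visceral HAPN activations between IBS-S and IBS-No S subjects".
- **Model.** Specific Aim 2, Analysis/interpretation, says: "Region of interest two-way ANOVA models will be developed in comparing" the change in activation, given as "baseline-DES activations, with IBS Group (IBS-S and IBS-No S) as a between-subject factor". The sample size section likewise powers a Group x Treatment effect.
- **Metric.** Data Analysis and Sample Size Calculations uses the strength of response, Delta S/S. Nothing relates this to a subject's own pre-treatment activation. No percentage, ratio or log scale is named, and baseline activation is not a covariate. The extra models under Aim 1, which carry over to Aim 2, cover disease duration, symptom severity and psychological features.

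The pilot found "significantly greater activation of the right prefrontal cortex, insula, and thalamus in the IBS-S subjects" compared with IBS-No S, and also greater bilateral anterior cingulate (ACC) and orbitofrontal activation. The ACC is the region used for the power calculation. The analysis section also foresees improvement in both groups and raises "the possibility that HAPN visceral activations are indeed partially refractory to desipramine in IBS-S". It puts this down to a smaller difference than expected, for which it would consider more enrolment.

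**The concern.** The groups are defined by somatization, not randomised, and are expected to differ before treatment in the quantity being measured. The plan never says whether response means units of signal removed or the share of the evoked response removed. With unequal starting levels these are different questions.

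If the drug acts proportionally, the post-treatment difference carries the baseline gap forward and favours Hypothesis 2, while the change score rewards the higher starting level and works against it. The same scans could be reported as IBS-S remaining abnormal or as IBS-S improving more, depending on which section is followed.

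Partial refractoriness, which the plan itself raises, can cancel out of the change score. The sample size section makes a null result more awkward, because it says that predicted non-significant interactions may be read as supporting the hypotheses.

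**Working it through.** **1. The plan's own figure.** The inputs are effect size 0.33, 20 per group, 10% attrition (18 per group) and Group x Treatment power 0.82. Alpha, sidedness, the type of effect size and the pre-post correlation are not stated. Reading 0.33 as Cohen's f, with two-sided 0.05 and zero correlation, noncentrality = f² x N x 2:

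- 20 per group: 0.1089 x 40 x 2 = 8.71, power 0.820.
- 18 per group: 0.1089 x 36 x 2 = 7.84, power 0.776.

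So 0.82 can be matched with 20 completers. The 0.95 for Group does not follow from the same settings, which give 0.82 for that test as well. I use 0.82 below only to set a plausible SD.

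**2. Algebra.** Let m be the IBS-No S baseline mean, R x m the IBS-S baseline mean, and pN and pS the proportional falls.

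- Change contrast: C = m x pN - R x m x pS. A positive value favours Hypothesis 2.
- Post-treatment contrast: D = R x m x (1 - pS) - m x (1 - pN). A positive value reads as persistent abnormality.
- Equal proportional response p: C = -m x p x (R - 1) and D = m x (1 - p) x (R - 1). For R above 1 the signs are opposite.
- C = 0 when pS/pN = 1/R, that is 80%, 67% and 50% at R = 1.25, 1.5 and 2.
- No response in IBS-S: C = m x pN, with no R in it.
- Equal additive fall in both groups: C = 0, so change is not distorted. D = m x (R - 1) is still the baseline gap.

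**3. Size on the change score (illustration).** Assumptions: 30% fall in IBS-No S, 18 per group, two-sided 0.05. The baseline m = 0.5 is arbitrary, since only ratios matter. Power 0.82 at zero IBS-S response needs d = 0.987 (noncentral t, 34 df), so the SD of change = 0.15/0.987 = 0.152.

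Half response has C = 0.15 - 0.5 x R x 0.15. Equal response has C = 0.15 - 0.5 x R x 0.30.

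| R | Half response: C | Power for Hypothesis 2 | Equal response: C | Significant larger fall in IBS-S, fixed SD | Same, SD scaling with baseline |
|---|---|---|---|---|---|
| 1 | 0.075 | 0.30 | 0 | 0.03 | about 0.02 |
| 1.25 | 0.056 | 0.19 | -0.0375 | 0.11 | about 0.09 |
| 1.5 | 0.0375 | 0.11 | -0.075 | 0.30 | about 0.20 |
| 2 | 0 | 0.03 | -0.15 | 0.82 | about 0.43 |

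Entries of 0.02 to 0.03 are the nominal 2.5% in one direction. The last column is simulated with a Welch test. At R = 2 and half response the expected contrast is exactly zero, so more subjects would not help.

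With zero response in IBS-S, C = 0.15 and power is 0.82 at every R with fixed SD. If the SD scales with baseline, C is unchanged but precision is lost. At R = 2 the case mirrors C = -0.15, so power is about 0.43.

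**4. Both scales together.** A separate simulation assumed a 40% fall in both groups, SD 0.5 of the IBS-No S baseline, pre-post correlation 0.5 and 18 per group (20,000 trials).

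| R | Post-treatment: IBS-S declared higher | Change: larger fall declared in IBS-S |
|---|---|---|
| 1 | 2.5% | 2.5% |
| 1.25 | 14% | 8% |
| 1.5 | 41% | 21% |
| 2 | 94% | 65% |

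**The case against.** **Proportional action is assumed.** Nothing in the documents says that desipramine removes a fixed share of the evoked response. If it acts additively, absolute change is the right scale. This stands, and it is why change should stay primary and the ratio be added as a sensitivity analysis.

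**The strict form of Hypothesis 2 is safe on the change score.** If IBS-S do not respond at all, the baseline ratio drops out of the contrast. This also stands. The difficulty is confined to partial or equal response, both of which the plan's analysis section entertains.

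**The baseline ratio is unknown.** Table 2 gives only Z and p values. For the ACC, Z of 2.67 and 4.15 with 8 per group implies standardised gaps of roughly 2.67 x √(2/8) = 1.3 and 4.15 x √(2/8) = 2.1, which do not give a ratio of means. Three of the ten regions showed no significant gap (left insula, left prefrontal cortex, left thalamus). Figure 5 expects raised visceral activation in IBS-No S as well. A ratio of 2 is therefore an upper illustration, not an expectation.

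**A reader might go further** and infer that absolute change is the only Aim 2 test and that it undermines Hypothesis 2 generally. The documents do not support that. The stated primary endpoint is the post-treatment difference, where a baseline gap errs in favour of the hypothesis, and full refractoriness leaves the change contrast undistorted.

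**Conclusion.** The concern holds in this form: the plan gives Aim 2 a post-treatment endpoint and a change-score model, expects unequal baselines, and fixes no scale. Under proportional drug action the two readings err in opposite directions, and partial refractoriness can disappear from the change score.

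The direction follows from algebra. The size does not follow from the documents, because neither the baseline ratio nor the percentage fall is given. On the assumptions shown, even a ratio of 1.25 cuts power under half response from 0.30 to 0.19. The chance of wrongly declaring a larger fall in IBS-S at ratio 2 is 0.82 with fixed SD, but about 0.43 if the SD scales with baseline, so the higher figure should not be quoted alone.

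**What to change.** 1. Reconcile Aim 2's Design and Methods and the Figure 9 legend with its Analysis/interpretation. Name the Group x Treatment contrast on change in visceral Delta S/S as the single primary test of Hypothesis 2, and make the post-treatment difference descriptive.
2. Pre-specify one sensitivity analysis from the same scans. For each group take mean week-4 over mean baseline visceral Delta S/S in the region of interest, and compare the groups as a ratio of ratios with a subject-level bootstrap 95% CI. Use group means, because individual baselines may be near zero.
3. Omit the ratio if the 95% CI of either group's baseline mean includes zero. In that case report absolute change only and say so.
4. Claim refractoriness, or its absence, only where the two scales agree in direction. Otherwise report the conclusion as scale-dependent.

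Adjusting for baseline by ANCOVA is not an automatic substitute, since the groups are not randomised and are expected to differ at baseline.

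The cost is a few lines of analysis text and one further estimate, with no new data. The downside is a wide CI for the ratio, and a real chance that the conclusion has to be reported as scale-dependent.
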